4.14 Immunogenicity Analysis

All ADA analyses will be performed on the Immunogenicity Analysis Set Population .

Participants in the placebo group will be pooled from each cohort for the summary analysis. ADA titer values will be summarized descriptively by dose cohort, including pooled placebo, pooled active treatment across cohorts, pooled IV cohorts, pooled SC cohorts and overall, by visit. Summary of ADA response to investigation product by visit and dose cohort, including pooled placebo, pooled

Statistical Analysis Plan

active treatment across cohorts, pooled IV cohorts, pooled SC cohorts and overall ADA response will be provided. A listing for immunogenicity analysis which including sampling date, time, day, ADA response category, ADA titer level and ADA maximum titer level will be presented.

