### 3. OBJECTIVES AND ENDPOINTS

Objectives	Endpoints
Primary	
To assess the safety and tolerability of ALXN1910	Incidence of TEAEs and TESAEs
Secondary	
To assess the PK of single ascending doses of ALXN1910	Serum ALXN1910 PK (activity) and PK parameters
To explore the PD effects of single ascending doses of ALXN1910	
 
Plasma concentrations of PPi, PLP, PL, and PA versus time profiles
 

To assess the immunogenicity of ALXN1910	Incidence and titers of treatment-emergent ADAs
To assess the absolute bioavailability of ALXN1910 SC	GMR of AUC values of SC versus IV from serum concentrations of ALXN1910
To compare the safety, tolerability, PK, and PD of ALXN1910 SC between Japanese and non-Japanese healthy participants	
 
Quantitative assessment of safety/tolerability and PK/PD parameters between Japanese and non-Japanese participants
 

Abbreviations: ADA = antidrug antibody; AUC = area under the serum concentration-time curve; GMR = geometric mean ratio; IV = intravenous; PA = pyridoxic acid; PD = pharmacodynamics(s); PK = pharmacokinetic(s); PL = pyridoxal; PLP = pyridoxal-5'-phosphate; PPi = inorganic pyrophosphate; SC = subcutaneous; TEAE = treatment-emergent adverse event; TESAE = treatment-emergent serious adverse event

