#### 9.4.2.3. Immunogenicity Analysis

All ADA analyses will be performed on the ADA Analysis Set Population using the ADA variables included in Section 8.9.1.

The incidence of ADA response categories will be summarized as absolute occurrence (n) and percent of all participants (%) by cohort. Participants in the placebo group will be pooled from each cohort for the summary analysis. Maximum ADA titer levels will be listed and summarized for ADA-positive participants as absolute occurrence (n) and percent of all participants (%). Additional details will be provided in the SAP.

Associations between ADA response categories and systemic exposure to study intervention may be explored for ALXN1910-treated participants by cohort, for analyzing the potential impact of immunogenicity on PK profiles. Additional details will be provided in the SAP.

Associations between ADA response categories and SAEs and severe adverse events may be explored, including SAEs such as systemic hypersensitivity, anaphylaxis, ISRs lasting more than 24 hours, and other immune-related SAEs.

Additional analysis may be performed with details to be provided in the SAP.

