4.2 General Presentation Considerations

This section is not applicable to PK data.

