4.2.6 Summary and Representation of Data

Continuous data will be summarized in terms of mean, standard deviation (SD), median, minimum, maximum, and number of observations, unless otherwise stated.

Categorical data will be summarized in terms of the number of participants providing data at the relevant time point (n), frequency counts, and percentages.

The minimum and maximum will be reported to the same number of decimal places as the raw data recorded in the database. The mean and median will be reported to one more decimal place than the raw data recorded in the database. The SD will be reported to two more decimal places than the raw data recorded in the database. In general, the maximum number of decimal places reported shall be four for any summary statistics.

Percentages will be presented to one decimal place. Percentages will not be presented for zero counts. Percentages will be calculated using N as the denominator. If sample sizes are small, the data displays will show the percentages, but any textual report will describe frequencies only. Percentage will be presented as whole number if value is 100.

If for any summary table, n is less than three then only n, mean, minimum, and maximum should be presented, and other summary statistics will be left blank.

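### The secondary endpoint is titers of treatment-emergent ADAs, but the only titer summary in SAP 4.14 pools all titers by cohort and visit, so no planned table reports it

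*SAP*

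**What the plan says.** Protocol section 3 and SAP 2.2 give the immunogenicity endpoint as "Incidence and titers of treatment-emergent ADAs".

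SAP 3.3.4 divides ADA-positive participants into three groups:
- pre-existing: positive at baseline, with later results negative or below 4-fold over the baseline titer;
- treatment-emergent: positive after dosing, with baseline negative or missing;
- treatment-boosted: positive at baseline and at least 4-fold higher after dosing.

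SAP 4.14 then plans a single titer summary: "ADA titer values will be summarized descriptively by dose cohort", with pooled placebo, pooled active, pooled IV, "pooled SC cohorts and overall, by visit". It also plans a summary of ADA response by visit and cohort, and a listing of response category, titer and maximum titer.

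SAP 4.14 names no statistics, so the default in SAP 4.2.6 applies: "Continuous data will be summarized in terms of mean, standard deviation (SD), median, minimum, maximum, and number of observations, unless otherwise stated". The only exclusion in SAP 4.2 is "This section is not applicable to PK data", so the default covers titers. For small cells, "If for any summary table, n is less than three then only n, mean, minimum, and maximum should be presented".

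**The concern.** The endpoint concerns antibodies that arise after dosing. A participant who was already positive before dosing and stays below the 4-fold threshold is not treatment-emergent under SAP 3.3.4, but that participant's titers enter the SAP 4.14 table as soon as any are reported. ADA samples are scheduled predose and on Days 29, 43 and 75, so one such participant can contribute at up to four visits. A cohort's titer row may then describe reactivity that the drug did not cause, and the number the endpoint asks for appears in no table.

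A lesser matter is the choice of statistics. Titers are read on a ratio scale, as the SAP's own 4-fold boosting rule shows, yet no geometric statistic is planned for them. PK concentrations in SAP 4.12.1 do have one. Below three values the default keeps the arithmetic mean and drops the median.

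**Working it through.** The documents state no expected titer, ADA rate or pre-existing rate, so there is no plan figure to reproduce. The main check compares the text. The arithmetic that follows uses assumed titers and rates.

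**1. Endpoint against table.**

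| Item | Endpoint (Protocol 3, SAP 2.2) | Titer summary (SAP 4.14) |
|---|---|---|
| Responses covered | Treatment-emergent | All titers |
| Split by SAP 3.3.4 category | Implied by the definition | None |
| Category and titer together | Needed | Listing only |

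The summary of ADA response can serve the incidence half of the endpoint. Nothing tabulates the titer half.

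**2. Effect of mixing (assumed titers).** Take three treatment-emergent titers of 10, 20 and 40: mean 70/3 = 23.3, median 20, geometric mean (10 × 20 × 40)^(1/3) = 20.0. Add one stable pre-existing titer X. The mean becomes (70 + X)/4 and the geometric mean (8000 × X)^(1/4).

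| X | Mean | Median | Geometric mean |
|---|---|---|---|
| 20 | 22.5 | 20 | 20.0 |
| 80 | 37.5 | 30 | 28.3 |
| 320 | 97.5 | 30 | 40.0 |
| 1280 | 337.5 | 30 | 56.6 |

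The effect runs from almost nothing to a mean 337.5/23.3 = 14.5 times too high. The median and geometric mean move less but still move, so a better choice of statistic does not cure the mixing. Only the split does.

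**3. Effect of one high titer (assumed titers).** Take six positives at 10, 10, 20, 20, 40 and T. The mean is (100 + T)/6.

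| T | Mean | Median | Geometric mean | T as share of sum |
|---|---|---|---|---|
| 80 | 30 | 20 | 22.4 | 44% |
| 320 | 70 | 20 | 28.3 | 76% |
| 1280 | 230 | 20 | 35.6 | 93% |
| 5120 | 870 | 20 | 44.9 | 98% |

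The mean follows T. The median stays at 20, and the printed maximum shows T openly.

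**4. How often cells fall below three.** Each cohort has 8 × 3/4 = 6 active participants. If only positives carry a titer, and each is positive with assumed probability p, then P(fewer than 3) = (1−p)^6 + 6p(1−p)^5 + 15p²(1−p)^4. This gives 98% at p = 0.1, 90% at 0.2, 74% at 0.3, 54% at 0.4 and 34% at 0.5. Cells under the small-n rule are therefore likely for most of that range. In them the median is blank, although with one or two values the minimum and maximum show every value.

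**The case against.** The best defence is that little is hidden. The listing gives category, titer and maximum titer, and with six active participants per cohort a reader can pick out the treatment-emergent titers by eye. The by-visit layout helps too: a stable pre-existing titer also shows at predose. SAP 4.12 plots PK by ADA category. No hypothesis is tested, and a table split by category would have mostly sparse cells. The documents also refer to TLF shells that are not included and might specify more. All of this stands, and it limits the gain. It does not supply a table of the endpoint.

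A reader might infer three stronger criticisms that the documents do not support.

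- **An undeclared departure from the protocol.** Protocol 9.4.2.3 says "Maximum ADA titer levels will be listed and summarized for ADA-positive participants", and SAP 4.14 only lists the maximum. But the protocol asks for that summary as counts and percentages, which fits the lower, moderate and high maximum-titer categories in Protocol 8.9.1. SAP 4.19 declares the removal of the titer-category analysis and gives small numbers as the reason.
- **Placebo mixed into cohort titers.** Pooled placebo is its own display group. At most it enters the overall column.
- **One high titer dominates the summary.** It dominates the mean and SD. The default also prints the median (when n is at least 3), minimum and maximum.

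**Conclusion.** The point holds as a mismatch between the endpoint and its planned summary. The endpoint is titers of treatment-emergent ADAs, the single titer summary ignores response category, and the endpoint can be read only from the listing. This follows from the text and needs no assumption.

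The numerical consequence does need assumptions. It depends on how many participants have pre-existing reactivity and at what titer, and the documents give neither. The mixing could be nil, and the figures above illustrate a range without predicting a result. The lack of a geometric statistic, and the loss of the median below n = 3, are secondary weaknesses that touch the mean and SD only. The point affects a descriptive secondary endpoint whose underlying data are fully listed. It should be corrected, but it does not threaten the study's conclusions.

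**What to change.** In SAP 4.14, replace the pooled titer summary with one based on each participant's maximum postdose titer, by cohort and by SAP 3.3.4 response category:

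- treatment-emergent as the endpoint row, with treatment-boosted and pre-existing on separate rows;
- n, median, geometric mean and range, with only individual values or the range when n is below 3, as a stated exception to SAP 4.2.6;
- a sentence saying that ADA-negative samples do not enter the titer statistics. A pre-existing participant whose postdose results are all negative is then counted in the category but contributes no postdose titer.

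The cost is a short change to SAP wording and one re-specified table. All the data are already collected. The downside is sparse cells, which the small-n rule above handles; the listing stays as planned.

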4.15 Biomarkers

Biomarker assays may be conducted as exploratory analyses on collected whole blood samples and the data used for research (eg, exploratory) related to ALXN1910. The results of biomarker analyses may be reported in the CSR or in a separate study summary.

4.16 Handling of Dropouts or Missing Data

No imputation of missing data will be performed except for partial dates imputation mention in Section 6.2.

4.17 Subgroup Analysis

No subgroup analysis is planned for the study.

4.18 Planned Interim Analyses

Interim analyses will not be conducted for this study.

4.19 Changes in the Conduct of the Study or Planned Analysis

The ADA titer categories analysis is removed as categories based on quartiles is not informative due to the small number of study participants.

6 APPENDICES

6.1 Schedule of Assessments

ALXN1910-HV-101

Statistical Analysis Plan

Table 5 Schedule of Assessments-Single Ascending Dose Cohorts (Screening through Day 5)

Study Day ^a	Screen -ing	Day -1		0		Da	y 2	Day 3		Day 4		Day 5				
Assessments	D -29 to D-2	Admit	Predose	0 h I/ SOI	30 min post I/SOI	2 h post I/SOI	4 h post I/SOI	8 h post I/SOI	12 h post I/SOI	24 h post I/ SOI	36 h post I/ SOI	48 h post I/ SOI	60 h post I/ SOI	72 h post I/ SOI	84 h post I/ SOI	96 h post I/SOI
Status (OP or CRU)	OP							C	RU							
Admission		Х														
Discharge																X ^b
Informed consent ^c	Х															
Inclusion/exclusion ^d	Х	Х														
Medical history ^e	Х															
Demographics	Х															
Height, weight, and BMI ^f	Х	Х														
Hepatitis B and C screen	Х															
HIV (Types 1 and 2) screen	Х															
Follicle-stimulating hormone ^g	Х															
Urine alcohol test	Х	Х														
Urine drug screen	Х	Х														
Serum pregnancy test ^h	Х															
Urine pregnancy		Х														

Alexion Pharmaceuticals, Inc.

ALXN1910-HV-101

Statistical Analysis Plan

test ^h																
Study Day ^a Assessments	Screen -ing D -29 to D-2	Day -1	Day 1								Day 2		Day 3		Day 4	
		Admit	Predose	0 h I/ SOI	30 min post I/SOI	2 h post I/SOI	4 h post I/SOI	8 h post I/SOI	12 h post I/SOI	24 h post I/SOI	36 h post I/SOI	48 h post I/SOI	60 h post I/SOI	72 h post I/SOI	84 h post I/SOI	96 h post I/SOI
Status (OP or CRU)	OP								CRU							
Randomization ⁱ			X													
Study intervention administration (ALXN1910 or placebo)				Х												
Injection/infusion site evaluation ^j				Х			X			Х		Х		X		Х
Physical examination	X	Х														
Brief physical examination ^k										X		X				X
Vital sign measurements ¹	X		X		Х	X	X	X	X	X		X		X		X
ECG ^m	Х		Х		Х	X	Х	Х	Х	X	Х	X		X		X
Chemistry ⁿ	Х	Х								X						X
Hematology ⁿ	Х	Х								Х						X
Coagulation ⁿ	Х	Х								Х						X
Urinalysis ⁿ	Х	Х								Х						X
PK°			X		X	X	X	X	X	Х		Х		Х		X

Alexion Pharmaceuticals, Inc.

ALXN1910-HV-101

Statistical Analysis Plan

PD (PPi, PLP, PL, and PA)	X		X	X	Х
---------------------------	---	--	---	---	---

Study Day ^a	Screen -ing	Day -1			Day 1						Day 2		Day 3		Day 4	
Assessments	D -29 to D-2	Admit	Predose	0 h I/ SOI	30 min post I/SOI	2 h post I/SOI	4 h post I/SOI	8 h post I/SOI	12 h post I/SOI	24 h post I/SOI	36 h post I/SOI	48 h post I/SOI	60 h post I/SOI	72 h post I/SOI	84 h post I/SOI	96 h post I/SOI
Status (OP or CRU)	OP				CRU											
Urine for calcium, phosphorus, and creatinine ^p			Х							Х		Х				Х
Immunogenicity samples ^q			Х													
Hypersensitivity reactions ^r				←Monitor continuously after dose→												
Hypersensitivity reaction laboratory tests (tryptase & complement C5b-9) ^s			Х	←See footnote ^r →												
Concomitant medications		←Monitor continuously (after ICF is signed at Screening)→														
Adverse events review and evaluation					←Monit	tor continu	uously (af	er ICF is	signed at	Screenin	g)→					

Note: When scheduled at the same timepoint, the triplicate ECG should be performed first, followed by vital signs assessments, and then PK/PD sampling.

ALXN1910-HV-101

Statistical Analysis Plan

^b Participants will be discharged from the CRU after completing all Day 5 assessments. Due to the time needed for turnaround of laboratory test results, discharge will actually occur on Day 6.

^c A signed and dated IEC-approved ICF must be obtained before any study-specific screening procedures are performed.

^d Recheck clinical status before randomization and/or dose of study intervention.

^e Including substance usage (drugs, alcohol, tobacco, and caffeine) and past/current medical conditions.

^f Height and BMI only at Screening.

^g Only female participants claiming postmenopausal status will have a follicle-stimulating hormone test to confirm postmenopausal status.

^h All female participants will have a pregnancy test (serum at Screening and urine on Day -1) to confirm the participant is not pregnant. Any female participant who becomes pregnant while participating in the study will be withdrawn.

ⁱ Randomization will occur predose on Day 1.

^j Injection/infusion site evaluations will be performed within 15 minutes after I/SOI and \pm 15 minutes at 4 and 24 hours post I/SOI. See Protocol Section 10.5 for additional details.

^k Brief physical examination to be conducted at discharge from the CRU.

¹ At Screening, supine and standing (orthostatic) blood pressures will be performed according to the CRU's typical procedure to exclude participants who are prone to orthostatic hypotension.

^m Each ECG timepoint during the study will be 12-lead and performed in triplicate sequentially within 5 minutes, at least 1 minute apart after 10 minutes of bedrest in supine position (note, no bedrest is required post ECG), at 90, 75, and 60 minutes before dosing. ECGs should not be performed after any major meal (i.e., major meals should be withheld until after ECG assessments).

ⁿ Investigators should review Day 5 laboratory results to ensure each participant is suitable for discharge.

° The IV dose cohorts will also have an end-of-infusion PK time point.

^p Spot urine collection.

^q Sample for ADA assessments will be collected prior to administration of the drug. In the event of suspected SAE like hypersensitivity or anaphylaxis, additional samples may be collected for ADA assessments at or near the event.

^r See Protocol Section 10.4 for details.

^s Collect 3 lab samples after a suspected hypersensitivity reaction: as soon as possible and at 2 and 8 hours after the suspected reaction (+ 1 hour window for each sample). If the suspected hypersensitivity reaction persists beyond 8 hours, the CRU should contact the Medical Monitor for guidance. Predose samples will only be analyzed for participants with a reported suspected hypersensitivity reaction.

Abbreviations: ADA = antidrug antibody; BMI = body mass index; C5b-9 = terminal complement complex; CRU = clinical research unit;

ECG = electrocardiogram; h = hours; HIV = human immune deficiency virus; I = injection; ICF = informed consent form; IEC = Independent Ethics Committee;

OP = outpatient; min = minutes; PA = pyridoxic acid; PD = pharmacodynamic; PK = pharmacokinetic; PL = pyridoxal; PLP = pyridoxal 5'-phosphate;

PPi = inorganic pyrophosphate; SOI = start of infusion; TEAE = treatment-emergent adverse event; TESAE = treatment-emergent serious adverse event

ALXN1910-HV-101

Statistical Analysis Plan

ALXN1910-HV-101

Statistical Analysis Plan

Schedule of Activities – Single Ascending Dose Cohorts (Day 6 through Day 75)

Study Day ^a	Day 6 post I/SOI	Day 7 post I/SOI	Day 8 post I/SOI	Day 15 post I/SOI	Day 22 post I/SOI	Day 29 post I/SOI	Day 36 post I/SOI	Day 43 post I/SOI (EOS/ED ^b)	Day 75 post I/SOI (EOS/ED ^b)
Status (OP or CRU)					0	Р			
Full physical examination								Х	Х
Brief physical examination			Х	Х		Х			
Vital sign measurements ^c			Х	Х		Х		Х	Х
12-lead ECG (triplicate) ^d	Х	Х	Х	Х				Х	Х
Chemistry			Х	Х	Х	Х	Х	Х	Х
Hematology			Х	Х	Х	Х	Х	Х	Х
Coagulation			Х	Х	Х	Х	Х	Х	Х
Urinalysis (via dipstick)			Х	Х	Х	Х	Х	Х	Х
Urine pregnancy test ^e						Х			
Serum pregnancy test ^e								Х	Х
РК	Х	Х	Х	Х	Х	Х	Х	Х	Х
PD (PPi, PLP, PL, and PA)			Х	Х	Х	Х	Х	Х	Х
Immunogenicity samples ^f						Х		Х	Х
Urine for calcium, phosphorus, and creatinine ^g			Х	Х		Х		Х	Х
Hypersensitivity reactions ^h	$\leftarrow Monitor \ continuously \ after \ dose \rightarrow$								
Hypersensitivity reaction laboratory tests (tryptase and complement C5b-9) ⁱ	$\leftarrow See \text{ footnote}^h \rightarrow$								
Concomitant medications	$\leftarrow Monitor \ continuously \ (after \ ICF \ is \ signed \ at \ Screening) \rightarrow$								
Adverse event review and evaluation	←Monitor continuously (after ICF is signed at Screening)→								

ALXN1910-HV-101

Statistical Analysis Plan

Note: When scheduled at the same timepoint, the triplicate ECG should be performed first, followed by vital signs assessments, and then PK/PD sampling.

^a Permitted windows for study assessments are described in the Windows Allowance Document.

^b EoS procedures will be performed on Day 75.. If possible, participants who withdraw/are withdrawn from the study should have an ED visit conducted at the time of discontinuation that includes the EoS assessments. All efforts will be made to contact participants who ED from the study via phone for a safety follow-up call approximately 30 days (4.5 half-lives) after their dose to assess AEs.

^c Vital signs taken postdose will be performed before the coinciding blood collection, whenever possible.

^d Each ECG will be 12-lead and performed in triplicate sequentially within 5 minutes, at least 1 minute apart after 10 minutes of bedrest in supine position (note, no bedrest is required post ECG). ECGs should not be assessed after any major meal (i.e., major meals should be withheld until after ECG assessments).

^e Only female participants of childbearing potential will have a pregnancy testing to confirm the participant is not pregnant.

^f Sample for ADA assessments will be collected prior to administration of the drug. In the event of suspected SAE like hypersensitivity or anaphylaxis, additional samples may be collected for ADA assessments at or near the event.

^g Spot urine collection.

^h See Protocol Section 10.4 for details.

ⁱ If the participant is in the clinic, collect the first sample as soon as possible (preferred) or within 1 hour of the suspected hypersensitivity reaction, and 2 additional samples at 2 and 8 hours after the suspected hypersensitivity reaction (+ 1 hour window for each sample). If the participant is not in the clinic, these samples do not need to be collected and suspected hypersensitivity reactions will be reported as TEAEs/TESAEs only. If the suspected hypersensitivity reaction 8 hours, the CRU should contact the Medical Monitor for guidance.

Abbreviations: ADA = anti-drug antibody; C5b-9 = terminal complement complex; CRU = clinical research unit; ECG = electrocardiogram; ED = early discontinuation; EOS = end of study; h = hours; I = injection; ICF = informed consent form; OP = outpatient; PA = pyridoxic acid; PD = pharmacodynamic; PK = pharmacokinetic; PL = pyridoxal; PLP = pyridoxal 5'-phosphate; PPi = inorganic pyrophosphate; SOI = start of infusion; TEAE = treatment-emergent adverse event; TESAE = treatment-emergent serious adverse event

6.2 Imputation Rules for Partial Dates

Imputed dates and time will NOT be presented in the listings.

Table 6 and Table 7 present algorithm for imputing partial dates for TEAE and prior/concomitant medication respectively.

Table 6	Algorithm f	r Treatment-Emergent Adverse Events:	

Start/Increase Severity Date	Stop Date	Action
Known	Known	Considered as a treatment-emergent adverse event (TEAE) if start date on or after the date of the first dose of investigational product (IP)
	Partial	Considered as a TEAE if start date on or after the date of the first dose of IP. The last day of the month and the last month (ie, December) will be used if the stop day/month is missing.
	Missing	Considered as a TEAE if start date on or after the date of the first dose of IP
Partial, but known components show that it cannot be on or after first IP taken date	Known	Not a TEAE. The first day of the month and January will be used if the start day/month is missing.
	Partial	Not a TEAE. The first day of the month and January will be used if the start day/month is missing. The last day of the month and the last month (ie, December) will be used if the stop day/month is missing.
	Missing	Not a TEAE. The first day of the month and January will be used if the start day/month is missing.
Partial, could be on or after first IP taken date	Known	Considered as TEAE, if stop date is after first IP taken date. The first IP taken date will be used if start date is in the same month/year with first IP taken date, or the first day of the month and January will be used if the start day/month is after first IP taken date Considered as not TEAE, if stop date is prior to first IP taken date. The first day of the month and January will be used if the start day/month is missing.
	Partial	Considered as TEAE. The first IP taken date will be used if start date is in the same month/year with first IP taken date, or the first day of the month and January will be used if the start day/month is after first IP taken date. The last day of the month and the last month (ie, December) will be used if the stop day/month is missing.
	Missing	Considered as TEAE. The first IP taken date will be used if start date is in the same month/year with first IP taken date, or the first day of the month and January will be used if the start day/month is after first IP taken date.
Missing	Known	Considered as TEAE if stop date is on or after the date of the first dose of IP.

Parexel International

Alexion Pharmaceuticals, Inc.

ALXN1910-HV-101

Statistical Analysis Plan

Start/Increase Severity Date	Stop Date	Action
	Partial	The last day of the month and the last month (ie,
		December) will be used if the stop day/month is
		missing. If the imputed stop date is on or after the first
		dose of IP considered as a TEAE; if the year is missing,
		considered as a TEAE
	Missing	Considered as a TEAE

Statistical Analysis Plan

Start Date	Stop Date	Action
Known	Known	If stop date is prior to the date for the first dose of IP, considered as prior; if stop date is on or after the date for the first dose of IP, considered as concomitant.
	Partial	The last day of the month and the last month (ie, December) will be used if the day/month of stop date is missing. If the impuated stop date is prior to the date for the first dose of IP, considered as prior; if the imputed stop date is on or after the date for the first dose of IP, considered as concomitant.
	Missing	Considered as concomitant.
Partial	Known	If stop date is prior to the date for the first dose of IP, considered as prior; If stop date is on or after the date for the first dose of IP, considered as concomitant. The first day of the month and January will be used if the start day/month is missing.
	Partial	The last day of the month and the last month (ie, December) will be used if the day/month of stop date is missing. If the impuated stop date is prior to the date for the first dose of IP, considered as prior; if the imputed stop date is on or after the date for the first dose of IP, considered as concomitant. The first day of the month and January will be used if the start day/month is missing.
	Missing	Considered as concomitant. The first day of the month and January will be used if the start day/month is missing.
	-	
Missing	Known	If stop date is prior to the date for the first dose of IP, considered as prior; if stop date is on or after the date for the first dose of IP, considered as concomitant.
	Partial	The last day of the month and the last month (ie, December) will be used if the day/month of stop date is missing. If the impuated stop date is prior to the date for the first dose of IP, considered as prior; if he imputed stop date is on or after the date for the first dose of IP, considered as concomitant.
	Missing	Considered as concomitant.

Table 7 Algorithm for Prior/Concomitant Medications Categorization:

Statistical Analysis Plan

